## **Statistical Methods**

Single factor ANOVA analysis will be used to determine if the extent of circumference reduction in the test group is statistically significant over changes in the control group. Additional correlation assessment will be performed to identify any potential relationships between patient data sets, and single-factor ANOVA assessment applied to those correlations as applicable. Missing or incomplete data shall be populated using least-favorable data from participants who did complete the study.

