### **Efficacy & Safety variables, including collection of adverse event data and anticipated adverse reactions**

#### **EFFICACY**

Input variables related to the determination of efficacy include the patient's age, gender, ethnicity, height, and weight (to determine the relative extent of obesity). Study output variables collected during this trial included the change in patient waist circumference as a primary indicator. Capture and collection of patient images may be useful for informational purposes, but are not a requirement of this study and shall not be used for any data analysis or study conclusions.

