### **Statistical methods planned, including handling data exclusion, analysis of sub-groups if any**

Any patient that did not conclude all three treatments shall be excluded from the analysis. If there are fewer than 37 patients remaining after the study concludes and exclusions are applied, than no analysis shall take place and additional study subject enrolled until a minimum of 40 completed participants exist. In the event that a patient concludes at least one treatment session, but afterwards discontinues

participation in the study, the presence of the patient in the study shall be acknowledged for data analysis purposes. Missing data for such acknowledged participants shall be fulfilled by inserting the least favorable result obtained realized from among all test subjects who did complete the study. Statistical analysis shall then proceed on the fully populated study data.

Primary analysis shall consist of applying the Anova single-factor acceptance test evaluating the change in waist circumference based on the data collected by the tape measure. A confidence of  $P=0.05$  shall be applied. The results of this data shall be directly applied to determining if the primary objective of the study has been met.

A correlation analysis shall be applied to all variable data recorded, as well as key calculations from the data, to identify any potential two-way connections or relationships between sets of data. Any correlations scoring a magnitude of 0.85 or greater shall be discussed and if appropriate, Anova single-factor analysis applied to determine if there is statistical significance to the relationship and any statements that might be supported by the data. Of primary interest is any impact the starting BMI might have on the amount of change, and any impact that gender may impart to the outcome.

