### **Sample size**

A total sample size of a minimum of 40 patients was established for this study. This number is based on

$$n = \frac{2 \cdot (Z_\alpha + Z_\beta)^2 \cdot \sigma^2}{d^2}$$

where:

$Z_\alpha = 1.96$ , based on a confidence of  $P=0.05$  (false rejecting of a true null hypothesis),  
 $Z_\beta = 0.84$ , based on a power of 80% (failure to reject a false null hypothesis),  
 $d = 1.0$  inch reduction in waist circumference as a meaningful/successful change in measurement,  
 $\sigma = 1.50$  inches, based on the evidence presented by a published study under similar treatment parameters and conditions reporting a typical response of 0.75 inches through the umbilical region and assuming some of the population may not respond at all.

The resulting calculation gives a population size of 37. Accounting for possible attrition and adding a generous margin of safety, a recruitment size of 50 individuals is arrived at. Review of the data analysis shall be conducted by an independent entity to confirm the handling and calculation of data, and the conclusions drawn from the data regarding statistical significance.

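### The primary ANOVA on waist change does not adjust for baseline waist: a cheap gain in precision is available if the trial has two arms

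*Combined protocol and SAP*

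**What the plan says.** The section *Statistical methods planned* describes the primary analysis as "applying the Anova single-factor acceptance test evaluating the change in waist circumference based on the data collected by the tape measure", at P=0.05. It does not name the factor. The synopsis (*Statistical Methods*) does: "Single factor ANOVA analysis will be used to determine if the extent of circumference reduction in the test group is statistically significant" relative to changes in the control group. Neither place lists a covariate, and no stratification factor appears anywhere.

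The data for adjustment are collected. *Methodology* and *Individual Treatment Session* both have waist measured before the first treatment. The *EFFICACY* section opens a list with "Input variables related to the determination of efficacy include" and goes on to age, gender, ethnicity, height and weight.

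The plan does look at some of these variables. *Statistical methods planned* singles out starting BMI and gender in a separate correlation analysis, in which correlations of 0.85 or more in magnitude are to be discussed.

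The design is described in two ways. The title page (randomised, placebo control), the synopsis (test and control groups) and *Sequence and duration of study period* (the patient's assigned study group) describe more than one group. *Study configuration* says that the study is single-arm and that all eligible candidates are treated.

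**The concern.** BMI has a floor of 25 and no ceiling, and both sexes are recruited, so starting waists will probably vary a good deal. If patients with larger waists tend to lose more, or if a high first reading tends to fall back on re-measurement, part of the spread in waist change is predictable from the first measurement. A one-factor ANOVA leaves that part in the error term. In a trial of about 20 per arm, the arms can also differ at baseline by chance, and the planned test does nothing about it.

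The correlation screen does not fill the gap. It is separate from the treatment comparison, and its threshold of 0.85 corresponds to 0.85² = 0.72 of variance explained. Covariate effects well below that could still matter for precision.

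At stake is some precision in the primary comparison and the credibility of any adjustment made later. A covariate chosen after the data are seen persuades few readers.

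**Working it through.** **Inputs from the *Sample size* section.** d = 1.0 ("inch reduction in waist circumference as a meaningful/successful change in measurement"). σ = 1.50 inches, justified by a published study "reporting a typical response of 0.75 inches through the umbilical region and assuming some of the population may not respond at all". Z values 1.96 and 0.84. Minimum 40 patients, recruitment 50.

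**Assumed, because the documents are silent.** 1:1 allocation. Correlation r between baseline waist and waist change within arm, 0.2 to 0.5. Baseline waist SD, 4 to 6 inches.

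**1. The plan's own figure.** 2 × (1.96 + 0.84)² × 1.50² / 1.0² = 2 × 7.84 × 2.25 = 35.28, so 36. The version based on the t distribution gives 37, which agrees with "The resulting calculation gives a population size of 37". This formula gives the number per arm, but the plan uses it as the total.

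**2. Unadjusted power at 20 v 20.** SE of the arm difference = 1.50 × √(2/20) = 0.474, and 1.0 / 0.474 = 2.11. With 38 degrees of freedom, power is 53.8% (55.9% by the normal approximation).

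**3. Adjusted power at 20 v 20.** Residual SD = 1.50 × √(1 − r²). The ideal information gain is 1/(1 − r²) − 1. The ideal column below uses only the smaller SD. The last two columns come from simulation with normal covariates and also charge for lost degrees of freedom and for chance correlation between covariate and arm. In the three-covariate model, independent covariates together explain r².

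| r | Residual SD | Ideal gain | Power, ideal | Power, baseline waist only | Power, three covariates |
|---|---|---|---|---|---|
| 0.2 | 1.470 | 4% | 55.5% | about 54% | about 52% |
| 0.3 | 1.431 | 10% | 57.7% | about 56% | about 54% |
| 0.4 | 1.375 | 19% | 61.1% | about 60% | about 58% |
| 0.5 | 1.299 | 33% | 66.0% | about 65% | about 62% |

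Against 54% unadjusted, one covariate roughly breaks even at r = 0.2 and gains about 11 points at r = 0.5. Three covariates lose about 2 points at r = 0.2 and break even near r = 0.3.

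**4. How large might r be?** If waist has the same SD at baseline and 12 weeks, and the two correlate at ρ, then r² = (1 − ρ)/2. That is the share of variance ANCOVA saves over the change score: 10% at ρ = 0.8 (r = 0.32), 5% at 0.9 (r = 0.22) and 2.5% at 0.95 (r = 0.16). Equivalently, r = SD of change / (2 × baseline SD), which is 1.50/8 = 0.19 at a baseline SD of 4 inches and 1.50/12 = 0.125 at 6 inches. Regression to the mean alone therefore puts r at or below the bottom of the table. The upper rows also need larger waists to lose more.

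**5. Chance imbalance.** At 20 per arm the standardised baseline difference has SD √(2/20) = 0.316, so a difference of 0.5 SD or more in a given covariate arises in about 11% of trials. With a baseline SD of 4 to 6 inches, a one-SE imbalance is 1.26 to 1.90 inches. At an assumed slope of 0.1 inch of change per inch of waist, it moves the raw arm difference by 0.13 to 0.19 inch. That is 0.27 to 0.40 of the SE in step 2.

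**6. Can adjustment restore 80% power?** By the normal approximation, the required R² is 1 − 20/35.28 = 0.43 (r about 0.66) with 40 patients, or 1 − 25/35.28 = 0.29 (r about 0.54) with 50, before any degrees-of-freedom cost. Both lie above the assumed range.

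**The case against.** The strongest case on the other side has four parts.

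- **The plan already uses these variables.** A reader might infer that baseline waist, BMI and sex are ignored. They are not. The outcome is change from baseline, so baseline waist enters by subtraction, and BMI and gender are examined in the correlation analysis. This part stands. What remains is that neither step adjusts the treatment comparison.
- **The planned test is valid.** A reader might infer that it is biased by chance imbalance. Under randomisation the unadjusted difference is unbiased on average, type I error is controlled, and chance imbalance is sampling variation already reflected in the standard error. This stands in full. The argument for adjustment is precision, and protection in the particular trial where the arms happen to differ.
- **Adjustment is not free.** It might seem natural to put baseline waist, sex and BMI all into the primary model. In a trial this small, three weak covariates can lower power (step 3), and BMI overlaps with waist. This stands, and it limits the recommendation to one covariate.
- **The design may be single-arm.** Then there is no arm comparison to adjust and no imbalance between arms. The mean change adjusted to the average baseline equals the raw mean, and a regression interval at the sample-average baseline treats that average as fixed, so it understates uncertainty. This also stands, and no adjustment is proposed for a single-arm study.

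**Conclusion.** The concern holds in a limited form. If the trial has two randomised arms, the primary test passes over a baseline measurement that is already collected and that could sharpen the comparison.

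At 20 v 20, power moves from 54% to between about 54% and 65% for r of 0.2 to 0.5. The ideal information gain is 4% to 33%, less a small degrees-of-freedom cost. These figures rest on the plan's d and σ and on assumed 1:1 allocation and assumed correlations. The documents support no particular r, and the low end, with essentially no gain, is quite possible.

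A reader might also infer that adjustment would rescue the trial's power. It would not within this range: the shortfall comes mainly from treating a per-arm sample size as the total, which is a separate and larger problem. This point is a cheap improvement and not a flaw that invalidates the analysis.

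**What to change.** First reconcile *Study configuration* (single-arm) with the title page, the synopsis *Statistical Methods* and *Sequence and duration of study period* (test and control groups).

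If two arms are confirmed, amend the synopsis and *Statistical methods planned* in the same words, before any unblinded data are seen:

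- The primary analysis is an ANCOVA of 12-week waist change on treatment group, with baseline waist as the one core covariate. State that baseline is the measurement taken before the first treatment, because waist is also measured before the later ones.
- Report the adjusted group difference with its 95% confidence interval and p-value, tested at 0.05.
- Keep the unadjusted single-factor ANOVA as a sensitivity analysis.
- Use a model that adds sex and baseline BMI as a sensitivity analysis only.

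Do not reduce the sample size on the strength of an assumed correlation.

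The cost is a few sentences and one degree of freedom, with no new data. The downside is essentially no gain, or a very small loss, if the correlation is low. If the study is confirmed as single-arm, this change falls away.

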### Patient population

The population for this study shall consist of adults age 18 and over. Recruiting efforts shall focus on obtaining a reasonably even number of male and female patients and to include patients exhibiting a body mass index (BMI) of 25 or higher. No concern or focus will be given regarding the ethnicity of the patients, although a wide range of ethnicities would be beneficial. Patients will be evaluated relative to the inclusion and exclusion criteria indicated below. A recruitment target of a total of 50 patients is established. During recruitment, each candidate will be assigned a test subject number for identification purposes.

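### The 0.85 correlation rule leaves starting BMI and gender, the plan's own questions of primary interest, with almost no chance of being discussed or tested

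*Combined protocol and SAP*

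**What the plan says.** The section on planned statistical methods, under Data Analysis, sets out this step in three sentences.

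- Scope: "A correlation analysis shall be applied to all variable data recorded, as well as key calculations from the data". No list of pairs is given.
- Trigger: "Any correlations scoring a magnitude of 0.85 or greater shall be discussed and if appropriate, Anova single-factor analysis applied".
- Priority: the relationships singled out as of primary interest are "any impact the starting BMI might have on the amount of change, and any impact that gender may impart to the outcome".

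The synopsis, under Statistical Methods, describes the same step with no threshold and without naming BMI or gender: "Additional correlation assessment will be performed to identify any potential relationships between patient data sets, and single-factor ANOVA assessment applied to those correlations as applicable".

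Two other sections bear on the point without adding an analysis. Under Patient population, "Recruiting efforts shall focus on obtaining a reasonably even number of male and female patients". The Efficacy section lists age, gender, ethnicity, height and weight as input variables. The Study Objectives section mentions neither BMI nor gender as a question to be answered.

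**The concern.** The plan names two relationships that matter most to it and then places them behind a screen that only a near-deterministic relationship would pass. The coefficients would be calculated, but below 0.85 nothing commits the sponsor to discuss or test them. A sizeable dependence of waist change on starting BMI or on gender could therefore go unreported. If it were reported, that would be a choice made after seeing the data.

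What is at stake is knowledge of who responds, not the trial's success claim. The primary and safety criteria do not use this rule.

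**Working it through.** **The plan's own figures.** The plan gives no derivation for 0.85. Its only calculation that bears on the point is the sample size, which fixes the n at which the rule operates: 2 × (1.96 + 0.84)² × 1.5² / 1.0² = 35.28, so 36. A t-based two-sample calculation gives 36.3, so 37, the stated figure. I use n = 40 (the stated minimum) and show 37 and 50 (the recruitment target).

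**Other inputs.** The 5% level comes from the same section ("A confidence of $P=0.05$ shall be applied"). The SD of 1.5 inches and the meaningful change of 1.0 inch come from Sample size. The 20/20 gender split is assumed from the recruitment aim. True correlations and true gender differences are assumed and shown as a range, because the documents give none.

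**How strict the screen is.**

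- Variance explained at the threshold: 0.85² = 0.7225, or 72%.
- Smallest correlation significant at two-sided 5%: r = t / √(n − 2 + t²). At n = 40, t = 2.024 and r = 2.024 / √(38 + 4.097) = 0.312. At n = 37 it is 0.325; at n = 50, 0.279.
- An observed r of 0.84 at n = 40 gives t = 0.84 × √(38 / (1 − 0.84²)) = 9.54, p = 1.2 × 10⁻¹¹. It would still miss the trigger.

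**BMI: chance of passing the screen** (simulated, bivariate normal, n = 40)

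| True correlation | Significant at 5% | Reaches 0.85 |
|---|---|---|
| 0.3 | 48% | 0 in 200,000 |
| 0.5 | 92% | about 2 per 100,000 |
| 0.7 | over 99.9% | 1.1% |
| 0.8 | about 100% | 18% |
| 0.88 | about 100% | 79% |

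For a true 0.7 the passing rate is 1.4% at n = 37 and 0.5% at n = 50.

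**Gender: the difference the screen requires.** With a balanced binary variable there are two readings of the 1.5-inch SD.

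- As the within-sex SD: 2r / √(1 − r²) = 1.70 / 0.527 = 3.23 SD, and 3.23 × 1.5 = 4.84 inches.
- As the total SD: 2r = 1.70 SD, and 1.70 × 1.5 = 2.55 inches.

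Simulated results at n = 40 (400,000 replicates; within-sex / total SD):

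| True difference | Significant at 5% | Reaches 0.85 |
|---|---|---|
| 1.0 inch | 54% / 59% | at most 1 in 400,000 under either reading |
| 1.5 inches | 87% / 95% | fewer than 10 in 400,000 under either reading |
| 2.0 inches | 98% / over 99.9% | about 0.005% / 0.2% |

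**Method.** The follow-on test is single-factor ANOVA. It does not suit continuous BMI without cut-points, and none are given.

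**The case against.** **The rule is a trigger, not a prohibition.** This is true. Both coefficients are computed, and nothing forbids discussing a smaller one. But nothing requires it either, so any such discussion would be selective.

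**The sentence on BMI and gender may stand alone**, with 0.85 meant only for the open scan; the synopsis, which has no threshold, leans that way. The reading is possible. It still leaves the two named questions with no defined analysis, and the same fix is needed.

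**A high threshold guards against chance findings.** It does for the scan: with an assumed 10 to 20 variables there are 45 to 190 pairs, and 5% of those is about 2 to 10 chance hits. That does not justify applying it to two questions named in advance.

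**The passing rates depend on assumptions.** They do. If only an active group of 20 were analysed (assumed), a true 0.5 would pass in about 0.25% of trials and a true 0.7 in about 6%, against a 5% critical value of 0.444. With a skewed, exponential-shaped BMI (assumed, since BMI is cut off at 25), a true 0.7 passes in about 3% and a true 0.88 in 68%. None of this changes the conclusion.

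**The matter is exploratory, the sample is small, and the protocol has larger conflicts**, such as single-arm against placebo-controlled. All of this is correct and limits the weight of the point. It does not remove it.

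**Conclusion.** The concern holds, as an exploratory-analysis defect that should be corrected. Followed as written, the rule leaves the plan's own named questions unanswered unless the relationship is close to deterministic: a true BMI correlation of about 0.88 is needed for roughly an 80% chance of passing at n = 40, and a gender difference of 2.55 to 4.8 inches is needed to sit at the threshold. Effects that an ordinary 5% test would usually detect would almost never trigger discussion.

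The threshold arithmetic for BMI needs no assumption beyond n. The gender difference rests on the 20/20 split and on how the 1.5-inch SD is read. The passing rates also rest on the assumed true effects and on normality. How often a real effect would be missed in this trial cannot be known from the documents. The conclusions on efficacy and safety are unaffected.

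**What to change.** Exempt starting BMI and gender from the 0.85 rule. Pre-specify one linear regression of 12-week waist change on starting BMI (continuous) and gender, and report both estimates with 95% confidence intervals whatever their size, labelled exploratory. Align the synopsis with this wording.

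The title page and synopsis describe a controlled comparison, while Study configuration describes a single arm. If the reconciled design has two arms, add group to the model, with exploratory group-by-BMI and group-by-gender terms.

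State the limits in the SAP. From tanh(2.80 / √(n − 3)), 80% power needs a correlation of about 0.43 at n = 40 (0.45 at 37, 0.39 at 50). For gender, 20 per sex gives 80% power at 0.909 SD, or 0.909 × 1.5 = 1.36 inches. Interaction terms are weaker: with 20 per group and correlations of 0.5 in the active group and 0 in control, the group-by-BMI term has about 34% power.

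The 0.85 screen may stay for the remaining all-pairs scan. The cost is SAP wording and one model: no new data, no extra patients and no change to the primary analysis.

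### Single-factor ANOVA is named as the significance test for correlations, but it does not test association between two continuous variables, and the BMI and gender questions may get no usable estimate (minor).

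*Combined protocol and SAP*

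**What the plan says.** The section on planned statistical methods (under DATA ANALYSIS) sets out a step after the primary analysis:

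- Scope: "A correlation analysis shall be applied to all variable data recorded, as well as key calculations from the data".
- Screen: "Any correlations scoring a magnitude of 0.85 or greater shall be discussed and if appropriate", after which comes the test.
- Test: "Anova single-factor analysis applied to determine if there is statistical significance to the relationship". The result also informs which statements the data might support.
- Focus: "Of primary interest is any impact the starting BMI might have on the amount of change, and any impact that gender may impart".

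The synopsis, under Statistical Methods, has the same step in shorter form: "single-factor ANOVA assessment applied to those correlations as applicable".

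Neither place defines the factor, the response or any grouping of a continuous variable. Neither names a test of a correlation coefficient or a regression. The 0.05 level is given for the primary analysis ("shall be applied. The results of this data shall be directly applied to determining if the primary objective" has been met), and none is given for the correlation step.

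**The concern.** Single-factor ANOVA compares the mean of a response across the levels of a factor. It suits a categorical factor. Most of what this trial records is continuous: age, height, weight, BMI, waist and waist change. For a pair of these there is no factor unless the analyst creates one. The most literal spreadsheet set-up is to enter the two columns as two groups, and that tests whether their means are equal, not whether the variables move together.

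The 0.85 screen adds a second problem. The pairs most likely to pass are related by construction: three weights and nine waist readings per patient (before and after each of three treatments, then three follow-ups), and BMI, which is computed from weight. The two questions that the plan singles out are unlikely to pass. At stake is whether the supplementary results answer the BMI and gender questions at all, and whether any p-value quoted beside a correlation refers to that correlation.

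**Working it through.** **Inputs from the documents.** Screen |r| ≥ 0.85. Calculated n = 37, minimum 40, recruitment 50. SD of waist change 1.50 inches and target change 1.0 inch (Sample size). BMI of at least 25 for every patient (inclusion criteria).

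**The plan's own figure.** 2 × (1.96 + 0.84)² × 1.50² / 1.0² = 35.28, rounded up to 36; the t-based version gives 36.3, rounded up to 37. The stated 37 is reproduced and is used below only as a value of n.

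**Assumed, not in the documents.** BMI mean 30, SD 4; waist mean 38 inches, SD 4. Ranges are shown where they matter.

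**1. What the screen already implies.** The direct test of a correlation is t = r√[(n − 2)/(1 − r²)]. For r = 0.85, 1 − r² = 0.2775.

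| n | t | p | smallest r with p < 0.05 |
|---|---|---|---|
| 37 | 0.85 × √(35/0.2775) = 9.55 | 2.8e-11 | 0.325 |
| 40 | 0.85 × √(38/0.2775) = 9.95 | 4.0e-12 | 0.312 |
| 50 | 0.85 × √(48/0.2775) = 11.18 | 5.8e-15 | 0.279 |

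At n = 37, the 95% CI for r = 0.85 is 0.73 to 0.92. A test after the screen can add nothing about chance. Correlations from about 0.31 to 0.85 would be significant at n = 40 but are never taken up.

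**2. ANOVA on two continuous columns.** With two groups of n, F = t² and t = (m₁ − m₂)/√[(s₁² + s₂²)/n]. The correlation does not appear in this formula.

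- BMI and waist change, n = 40: t = (30 − 1)/√[(16 + 2.25)/40] = 42.9. Every BMI is at least 25, so the mean is too. Even with mean BMI 25, SD 8 and mean change 3 inches, t = 22/√[(64 + 2.25)/40] = 17.1. The result is significant whatever the correlation.
- Two waist readings one inch apart (38 and 37), n = 40: t = 1/√(32/40) = 1.12, p = 0.27. With SD 3, p = 0.14; with SD 6, p = 0.46. A one-inch gap reaches p < 0.05 only if the SD is below 1/(1.991 × √(2/40)) = 2.25 inches.

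Simulation at n = 40 (5,000 runs), share of runs with p < 0.05:

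| Pair | two-column ANOVA | Pearson test |
|---|---|---|
| BMI and change, ρ = 0 | 100% | 4.5% |
| BMI and change, ρ = 0.9 | 100% | 100% |
| Waist 38 and 38, ρ = 0.9 | 0% | 100% |
| Waist 38 and 37, ρ = 0.9 | 1.2% | 100% |

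**3. Where ANOVA is valid.** Waist change by gender: in a simulated data set, ANOVA and the point-biserial correlation gave the same p (0.5575). Waist change by BMI tertile (n = 39): 4.7% rejection at ρ = 0, 73% at ρ = 0.5 and 100% at ρ = 0.85. The F test of a regression gave the same p as Pearson (0.00934), but that is not the usual meaning of single-factor.

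**4. Would the BMI and gender questions pass 0.85?**

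- Gender, even split: the means must differ by 2r/√(1 − r²) = 1.70/0.527 = 3.23 within-gender SDs. If 1.50 inches is the within-gender SD, that is 3.23 × 1.50 = 4.84 inches. If 1.50 is the overall SD, it is 2 × 0.85 × 1.50 = 2.55 inches. Both are well above the 1.0 inch target change.
- BMI: r = 0.85 means that BMI explains 0.85² = 72% of the variance of waist change. If the true correlation were 0.5, the observed r at n = 40 would have to lie (1.256 − 0.549) × √37 = 4.30 standard errors above it on the Fisher z scale to pass.

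**The case against.** The best defence has four parts.

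- **ANOVA is right for gender, and can be right for BMI in groups.** This stands. A reader might infer that the ANOVA p-value says nothing about any relationship in the plan; step 3 shows that this is too broad. The defect is confined to continuous pairs. For grouped BMI, no cut points are given, and choosing them after seeing the data would be an avoidable freedom.
- **The two-column layout is not written anywhere.** This also stands. The sections on data analysis and data quality assurance put the work in electronic spreadsheets, which makes that layout plausible but does not specify it. What the documents show is a test named without a set-up that would make it test a correlation.
- **The 0.85 screen stops chance findings.** This stands. A reader might infer that the plan could support false statements from unrelated variables. It would not: a pair with r near zero never reaches the ANOVA. The reachable error goes the other way, a non-significant result for a strongly related pair, and it falls mainly on repeated readings on one scale, where significance means little anyway.
- **The wording is conditional, and independent statistical review is planned.** This lowers the risk. But no criterion says when the ANOVA is appropriate, and a reviewer would be checking against the same unspecified step.

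**Conclusion.** The point holds in limited form and is minor. For two continuous variables, the named test does not address the association. After a screen that already implies p of about 3e-11 at n = 37, it can only be redundant, answer a different question, or wrongly deny a strong relationship. The more practical loss is that starting BMI and gender would rarely pass 0.85 and so may get no usable estimate.

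A reader might also infer that the efficacy conclusion is at risk. The documents do not support that: the primary objective is tied to the separate waist-change analysis, and the synopsis calls the correlation step additional.

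The conclusion rests on the usual meaning of single-factor ANOVA. The simulated rates depend on assumed means and SDs, but the BMI result follows from the BMI limit of 25 over the range shown, and the waist result holds for any SD above about 2.25 inches. The gender figures assume an even split, which recruitment aims for approximately. That BMI would rarely reach 0.85 is a judgement based on the variance share that this requires.

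**What to change.** In the synopsis (Statistical Methods) and in the planned statistical methods under DATA ANALYSIS:

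1. For pairs of continuous variables, replace single-factor ANOVA with the correlation or regression slope and its 95% CI.
2. Report starting BMI and gender against week-12 waist change whatever the size of the correlation: a slope with 95% CI for BMI, and ANOVA or a t-test with the mean difference and 95% CI for gender.
3. Leave out pairs where one variable repeats the other or is computed from it.
4. Label all of these results exploratory.

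The cost is a few sentences in two places. The data, software and sample size do not change.
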